	
Beginning with protocol version 20181218, patients who are MGMT unmethylated will only receive one adjuvant cycle of the TMZ regimen according to their assigned randomized arm. Patients who are MGMT methylated or whose methylation status is inconclusive will continue with up to 12 cycles of TMZ. All patients enrolled prior to approval of protocol version 20181218 will receive 6-12 cycles of TMZ, independent of their MGMT methylation status. Patients who are dependent on steroid supplements above immune suppressive levels (4 mg) at time of vaccination or who are unable to tolerate TMZ will be withdrawn from the study and replaced before vaccination.
 
Up to 70 patients may be consented on the main informed consent to meet the goal of 26 evaluable patients (13 per arm) for the primary outcomes.
 
For both arms, the patients must be screened at Duke within 3 ± 1 weeks after the completion of standard of care radiation. For both arms, the initial cycle of adjuvant TMZ will begin as soon as possible following randomization. For Arm 1, the adjuvant TMZ cycle(s) will be given at a standard targeted dose of 150-200 mg/m²/d for 5 days. For Arm 2, the adjuvant TMZ cycle(s) will be at the dose-intensified dose of 75-100 mg/m²/d for 21 days. If a patient enrolls after approval of protocol version 20181218 and has an MGMT unmethylated tumor, they will discontinue TMZ after the 1st cycle.
 
All patients will have blood drawn for immune monitoring and then receive a tetanus pre-conditioning injection intradermally (i.d.) in the RIGHT groin (as described below) on day 22 (+1 day) of cycle 1 of adjuvant TMZ. On the following day, the patients will receive study vaccine. The vaccine is administered as follows: 500 µg of PEP-CMV Component A mixed with Montanide ISA-51 administered i.d. with half on the right groin and half on the left groin. Vaccines #2 and #3 will be given at 2 week (+ 3 days) intervals; the MRI visit with immune monitoring will take place within 2 weeks (+3 days) of vaccine #3. Prior to the 20181218 amendment, vaccination consisted of two components: Component A and Component B. However, after that amendment, vaccination for all newly enrolled patients consisted of Component A only.
 
For patients enrolled before approval of protocol version 20181218 and for patients enrolled after approval of protocol version 20181218 who have an MGMT methylated tumor or MGMT methylation status in inconclusive, TMZ cycle 2 will begin after that visit, but no sooner than 14 days post vaccine 3. This will result in at least ~35-day delay before starting TMZ cycle 2. MGMT unmethylated patients enrolled after approval of protocol version 20181218 will not receive subsequent cycles of TMZ, but will continue to receive vaccines approximately every 4 (+2) weeks.
 
An unacceptable toxicity will be defined as any \geq Grade 3 toxicity possibly, probably, or definitely related to the PEP-CMV vaccine with the following exceptions. A portion of the Grade 3 vaccine reactions noted in prior patient experiences with the PEP-CMV vaccine, described in Sections 11.5.1 and 14.2.1, will not be considered unacceptable if they are indicative of immune response. That is, toxicities such as Grade 3 flu-like symptoms, fever, and chills/rigors will not be considered unacceptable toxicities if the duration is less than 72 hours. Any \geq Grade 3 organ toxicity (cardiac, renal, hepatic), including CRS-related toxicities such as hypotension and

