--	---

	
tachycardia, of any duration will be considered an unacceptable toxicity. Although not considered an unacceptable toxicity, any patient with \geq Grade 2 urticaria will not receive further vaccines, will be withdrawn from the study, and will be replaced if less than 3 vaccines have been administered without unacceptable toxicity. The prevalence of unacceptable toxicities occurring during the initial 3 bi-weekly vaccinations or the vaccinations administered concurrently with temozolomide will be continuously monitored. If more than 25% of accrued patients experience unacceptable toxicities, then accrual will be suspended and reported toxicity will be carefully reviewed to determine if modifications to the protocol treatment should occur. Peptide vaccinations employing Montanide ISA-51 as adjuvants have generally been well-tolerated in human patients in numerous phase I-III trials.
 
Treatment Plan: Patients will be vaccinated in conjunction with subsequent 28-day cycles for a total of 6 to 12 adjuvant TMZ cycles after RT if patient is continuing on TMZ (i.e., for patient's who's tumor is methylated or the status is inconclusive). Cycles are every 4 (+ 2) weeks, adjusting for slight delays on startup or scheduling of each 28-day cycle. For patients whose tumor is methylated or the status is inconclusive, the total number of TMZ cycles given will be at the discretion of the treating oncologist. During the 28-day cycles, vaccinations will occur on day 23 (-1 day, + 2 days) of each cycle for each arm: (Arm 1) standard TMZ (200 mg/m²/day on days 1-5 of each 28-day cycle), or (Arm 2) dose-intensified TMZ (100 mg/m²/day on days 1-21 of each 28-day cycle).
 
All vaccines will be given i.d. approximately 10 cm below the inguinal ligament bilaterally. Component A will be administered half in the RIGHT groin and half in the LEFT groin at a maximum of 0.2 mL per intradermal injection. A target of six cycles with maximum of twelve cycles of TMZ may be given to patients enrolled before approval of protocol version 20181218 and to methylated patients enrolled after approval of protocol version 20181218, at the discretion of the treating neuro-oncologist. Unmethylated patients enrolled after approval of protocol version 20181218 will receive only one cycle of TMZ. After the completion of a patient's last TMZ cycle, vaccines will continue every 4-6 weeks for a maximum number of 20 vaccines (unless tumor progression occurs).
 
Patients will be imaged with contrast-enhanced MRI within 2 weeks (+3 days) after vaccine 3 and then approximately every 8 weeks [every 2 cycles thereafter (i.e., end of cycles 3, 5, 7, 9, 11)]. RANO criteria will be used for assessment of pseudo-progression, and patients demonstrating definitive progression will be removed from study. Any patient removed prior to immune monitoring post vaccine 3 will be replaced for immunologic endpoints. Clinical endpoint comparisons will be made amongst patients successfully randomized to adjuvant TMZ treatment arms and receiving at least one vaccine.
 
Blood for immune monitoring will be obtained:
 
• Prior to Td pre-conditioning• During vaccines 1 and 2 (just prior to Component A, 1 and 2 hours after Component A)• Prior to vaccine 3• After vaccine 3 (within 2 weeks of vaccine 3 [+ 3 days])• Prior to vaccines 4 and 6

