Patients who receive more than 1 cycle of TMZ will be vaccinated in conjunction with each **subsequent** 28-day TMZ cycle for a total of 6 to 12 cycles of TMZ after RT followed by further vaccination up to 20 vaccines. Patients who receive only 1 cycle of TMZ will be vaccinated on a 28-day cycle with up to 20 vaccines. All cycles, with or without TMZ, may be given every 4 (+ 2) weeks, in order to adjust for slight delays on startup of each 28-day cycle, and the total number of cycles are given at the discretion of the treating oncologist. During vaccine (+/- TMZ) cycles, vaccinations will occur on day 23 (-1 day, + 2 days) of each cycle for each arm: (Arm 1) standard TMZ (150-200 mg/m²/day on days 1-5 of each 28-day cycle), or (Arm 2) dose-intensified TMZ (75-100 mg/m²/day on days 1-21 of each 28-day cycle). All vaccines will be given i.d. approximately 10 cm below the inguinal ligament bilaterally. A target of six cycles with a maximum of twelve cycles of TMZ may be given to patients enrolled prior to approval of protocol version 20181218 and those with MGMT/inconclusive methylation status if enrolled after approval of protocol version 20181218, at the discretion of the treating neuro-oncologist. After the completion of a patient's TMZ cycles, vaccines will continue to be administered every 4 (+ 2) weeks for a maximum of 20 vaccines (unless tumor progression occurs).

Patients will be imaged with contrast-enhanced MRI after vaccine 3 (at cycle 2 initiation visit) and then approximately every 8 weeks [every 2 cycles thereafter (i.e., end of cycles 3, 5, 7, 9, 11)]. RANO criteria [111] will be used for assessment of pseudoprogression and patients demonstrating definitive progression will be removed from study. Any patient removed prior to immune monitoring post vaccine 3 will be replaced for immunologic endpoints. Clinical endpoint comparisons will be made amongst patients randomized to adjuvant TMZ treatment arms who have received at least one vaccine.

Blood for immune monitoring will be obtained:

- Prior to Td pre-conditioning
- During vaccines 1 and 2 (just prior to Component A, 1 and 2 hours after Component A)
- Prior to vaccine 3
- After vaccine 3 (within 2 weeks of vaccine 3 [+ 3 days])
- Prior to vaccines 4 and 6
- At tumor progression (if feasible)

Patients seen by the Duke neuro-oncology team between these vaccine visits may have blood drawn for immune monitoring at the discretion of the study team.

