11.5.4 Unacceptable Toxicities

The original definition of unacceptable toxicities in this study was any vaccine-related or any non-neurologic \geq Grade 3 toxicity of any duration not attributable to TMZ, bevacizumab, and/or disease progression; any Grade 4 toxicity, including neurologic events not due to progressive disease; or any life threatening-event not attributable to concomitant medication, co-morbid event, or disease progression. The definition of unacceptable toxicity was revised with v.20200117 of the protocol and will be defined now as any life-threatening \geq Grade 3 toxicity that is possibly, probably, or definitely related to the PEP-CMV vaccine with the following exceptions (updated in the v.20200504 protocol). A portion of the Grade 3 vaccine reactions noted in prior patient experiences with the PEP-CMV vaccine, described in Sections [11.5.1](#) and [14.2.1](#), will not be considered unacceptable if they are indicative of immune response. That is, toxicities such as Grade 3 flu-like symptoms, fever, and chills/rigors will not be considered unacceptable toxicities if the duration is less than 72 hours. Please see Section [11.5.1](#) for guidelines on management of immune response, including cytokine release syndrome (CRS). Any \geq Grade 3 organ toxicity (cardiac, renal, hepatic), including CRS-related toxicities such as hypotension and tachycardia, of any duration will be considered an unacceptable toxicity. Toxicities will be tracked on all subjects who received PEP-CMV vaccine using the NCI CTCAE (Version 4.03) criteria. Patients who experience unacceptable toxicities will not continue to receive vaccine therapy. Although not considered an unacceptable toxicity, any patient with \geq Grade 2 urticaria will not receive further vaccines, will be withdrawn from the study, and will be replaced if less than 3 vaccines have been administered without unacceptable toxicity.

The prevalence of unacceptable toxicities occurring during the initial 3 bi-weekly vaccinations or the vaccinations administered concurrently with temozolomide will be continuously monitored. If more than 25% of accrued patients experience unacceptable toxicities, then accrual will be suspended and reported toxicity will be carefully reviewed to determine if modifications to the protocol treatment should occur. Peptide vaccinations employing Montanide ISA-51 as adjuvants have generally been well tolerated in human patients in numerous phase I-III trials.

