11.10.2 Follow-up Requirements for Early Withdrawal

Subjects that are withdrawn by the PI prior to randomization will be considered eligibility failures and thus not followed for survival.

Randomized subjects treated on this study that are withdrawn by the PI for any of the aforementioned reasons after the immune monitoring post-vaccine 3 will continue to be followed for progression and survival by the study team until death or are lost to follow up unless the subject voluntarily withdrew permission to follow for survival.

Randomized subjects that withdraw before the immune monitoring post-vaccine 3 will be followed for survival by the study team unless permission to do so has been withdrawn.

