11.10.3 Replacement of Early Withdrawal(s)

Subjects who voluntarily withdraw prematurely or who are withdrawn by the PI prior to immune monitoring post vaccine #3 will be replaced. However, the data from these patients will be included in all appropriate analyses.

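### The urticaria exemption has no upper grade, so Grade 3+ urticaria can go uncounted in the primary safety percentage; withdrawing the patient also gives up a scheduled post-vaccine-3 draw

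*Combined protocol and SAP*

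**What the plan says.** **Exemption.** Section 11.5.4 deals with urticaria in one sentence. It opens "Although not considered an unacceptable toxicity, any patient with" urticaria of Grade 2 or higher, ends vaccination, and adds that the patient "will be withdrawn from the study, and will be replaced if less than 3 vaccines have been administered without unacceptable toxicity". The synopsis has the same sentence ("Grade 2 urticaria will not receive further vaccines, will be withdrawn from the study, and will be replaced if less than 3 vaccines"). Neither place gives an upper grade.

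**General definition.** The two places differ. The synopsis sets the bar at or above "Grade 3 toxicity possibly, probably, or definitely related to the PEP-CMV vaccine with the following exceptions". Section 11.5.4 reads "The definition of unacceptable toxicity was revised with v.20200117 of the protocol and will be defined now as any life-threatening" toxicity of at least Grade 3, again with a possible or stronger relation to the vaccine. Both then exempt Grade 3 flu-like symptoms, fever and chills or rigors that last under 72 hours. Both count cardiac, renal or hepatic toxicity of Grade 3 or higher, including hypotension and tachycardia, whatever its duration.

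**Use of the definition.** Section 15.4.1 makes the per-arm percentage with unacceptable toxicity, among all vaccinated patients, the primary safety analysis. The synopsis, 11.5.4 and 15.3 suspend accrual when the proportion passes 25%.

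**Draw and replacement.** Section 11.8 makes a patient evaluable only if immune monitoring is done after vaccine 3. Table 3 places that draw two weeks (+3 days) after vaccine 3. Section 11.1 states: "Any patient removed prior to immune monitoring post vaccine 3 will be replaced for immunologic endpoints". Section 11.10.3 says that subjects "withdrawn by the PI prior to immune monitoring post vaccine #3 will be replaced". Section 11.10.2 says: "Randomized subjects that withdraw before the immune monitoring post-vaccine 3 will be followed for survival by the study team". It provides progression follow-up only for those withdrawn after the draw.

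**The concern.** Safety is a primary objective, and its numerator is the count of unacceptable toxicities. A vaccine reaction severe enough to end vaccination for good should not fall out of that count through a sentence with no grade ceiling. The neighbouring exception for flu-like symptoms is bounded by grade and duration and has a stated reason (signs of immune response). The urticaria sentence has no such bounds and no reason, although 14.2.1 lists hives among the possible allergic reactions to PEP-CMV.

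The same sentence takes the patient out of the study, not just off vaccine. If the urticaria follows vaccine 3, the patient has had all the vaccine that the ELISPOT endpoint needs, and the draw is already scheduled. Leaving before it costs a primary-endpoint observation, and progression follow-up is then not required.

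**Working it through.** **1. What the exemption changes under each definition.** Each cell shows whether a vaccine-related event counts as unacceptable without the urticaria sentence, then with it.

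| Event | Synopsis | 11.5.4 |
|---|---|---|
| Grade 2 urticaria | no / no | no / no |
| Grade 3+ urticaria, not life-threatening | yes / **no** | no / no |
| Life-threatening Grade 3+ urticaria | yes / **no** | yes / **no** |
| Grade 3+ hypotension, tachycardia or organ toxicity alongside urticaria | yes / yes | yes / yes |

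The sentence changes the count in three cells: both kinds of Grade 3+ urticaria under the synopsis, and only the life-threatening kind under 11.5.4.

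**2. Size in the safety percentage (illustration).** The documents give no urticaria rate, so I take one uncounted case. Exact (Clopper-Pearson) limits for x events in n patients are the 2.5% quantile of Beta(x, n − x + 1) and the 97.5% quantile of Beta(x + 1, n − x); the lower limit is 0 when x = 0.

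- n = 13: 0/13 = 0% (0 to 24.7%); 1/13 = 7.7% (0.2 to 36.0%).
- n = 26: 0/26 = 0% (0 to 13.2%); 1/26 = 3.8% (0.1 to 19.6%).

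Thirteen is the evaluable target per arm. The safety set is everyone vaccinated, so 13 is a low denominator, and the shift shrinks as it grows.

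**3. The 25% rule.** One uncounted event matters only at the threshold.

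- 15 patients (the number given Component A only by 20200110, per 15.1): 0.25 × 15 = 3.75. So 3/15 = 20.0% does not suspend accrual and 4/15 = 26.7% does.
- 26 patients: 0.25 × 26 = 6.5. So 6/26 = 23.1% does not and 7/26 = 26.9% does.

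Section 15.3 reports no unacceptable toxicity under the revised definition at v.20200117.

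**4. The post-vaccine-3 draw.** The draw is due at most 14 + 3 = 17 days after vaccine 3. The urticaria sentence counts vaccines given (fewer than three), while 11.1 and 11.10.3 look to whether the draw was done. A patient with three vaccines and no draw is not replaced by the urticaria sentence, but is replaced by the general rules. The sentence says that replacement follows if fewer than three vaccines were given; it does not say only if. The rules are compatible, 13 evaluable patients per arm can still be reached, and the planned 81% power is unaffected. That 81% cannot be recomputed, because the individual ACT II titers are not given, but nothing here rests on it. The cost is one avoidable replacement: at the planned maximum, 70/26 = 2.7 consents per evaluable patient. This is an upper figure, because 70 is a ceiling.

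**5. Progression data.** Section 15.4.4 centres PFS on patients with at least three vaccines, timed from the third. This patient fits that set, yet 11.10.2 asks only for survival follow-up. If 11.8 governs instead (survival analyses in evaluable patients), the patient leaves the set. Either way the progression information is not secured.

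**The case against.** **Only Grade 2 may have been meant.** Urticaria is not listed with the flu-like exceptions. It comes later, in a sentence about stopping vaccine, and the opening clause may only explain why a Grade 2 event, below the Grade 3 bar, still ends vaccination. The amendment log entry for 20180719 also speaks of Grade 2 urticaria as a withdrawal criterion. This is fair evidence of intent, and no intended exemption of severe urticaria is shown. But the current sentence covers Grade 2 and above, and a reader who applies it would leave Grade 3 out.

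**The body text decides, and there the point nearly vanishes.** Section 15.3 sends the reader to the body definition (cited as 11.5.3, now 11.5.4). This stands: a reader might infer that all severe urticaria is hidden under any reading, and the documents do not support that. Under 11.5.4, non-life-threatening Grade 3 urticaria is excluded by the life-threatening qualifier, not by this sentence. That mismatch with the synopsis affects every Grade 3 toxicity and is a separate issue.

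**The events are not lost.** This also stands. Section 11.5.5 keeps a summary of all adverse events by grade, 14.3 calls for action on an unexpected frequency of Grade III or IV events, and vaccine stops for the patient anyway.

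**The draw is handled.** A reader might infer that the ELISPOT comparison loses power. It does not, because the synopsis, 11.1 and 11.10.3 all replace a patient removed before the draw. Nor is the draw forbidden: 11.1 and 13 allow discretionary immune-monitoring blood between vaccine visits. What remains is that nothing requires it once the patient is withdrawn.

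**Conclusion.** The point holds in a limited form, as an optional improvement. The exemption lacks a ceiling, so whether Grade 3+ urticaria enters a primary safety estimate depends on which definition is applied: all such cases are left out under the synopsis, only life-threatening ones under 11.5.4. The illustrated shift is 0/13 versus 1/13, and the suspension decision changes only at the threshold. This assumes a case occurs without Grade 3+ organ toxicity, which would count by itself. The reaction lists in 11.1 and 14.2.1 name no urticaria case; the opening of 11.5.1 was not available for this check. The expected effect is small.

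On the draw, there is no power loss. The cost is an avoidable replacement, and the ELISPOT and PFS data lose a patient who reacted to the vaccine. A reader might go further and infer a bias in the arm comparison. The documents give no urticaria rate by arm and do not relate urticaria to ELISPOT response, so neither its presence nor its direction can be claimed.

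**What to change.** Put identical wording in the synopsis and 11.5.4:

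> Grade 2 urticaria is not an unacceptable toxicity but stops further vaccine. Vaccine-related urticaria of Grade 3 or higher is an unacceptable toxicity and stops further vaccine. A patient who has had vaccine 3 still gives the scheduled post-vaccine-3 draw and is followed for progression and survival; a patient without that draw is replaced under 11.10.3.

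Naming Grade 3+ urticaria outright makes its count the same under either general definition; sending it back to the general definition would not, while the two differ. The protective stop at Grade 2 stays, withdrawal from the study goes, and the missing draw becomes the only replacement trigger. The life-threatening mismatch still needs its own correction.

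**Cost.** A protocol amendment with IRB approval (17.6) and, as an assumption, notification under the IND, since the log says the definition was last revised at FDA request. It can be bundled with the next amendment. No visit is added: the draw falls within 17 days of vaccine 3, inside the month after final vaccination that 11.7 sets as a limit for the treatment phase. The reported unacceptable-toxicity percentage may rise slightly.

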11.5.5 Adverse Event Reporting and Documentation

An “Adverse Event” will be defined as any adverse change from the subject’s pre-treatment baseline condition (which is based on the physical and neurologic assessment done at the SOC clinic visit prior to initiation of post-radiation chemotherapy and vaccine therapy), including any clinical or laboratory test abnormality that occurs during the course of research **after** vaccine treatment has started. Adverse events will be categorized and graded in accordance with the NCI CTCAE (Version 4.03).

A “Serious Adverse Event” will be defined as an undesirable sign, symptom or medical condition which: 1) is fatal or life threatening; 2) requires inpatient hospitalization or a prolongation of existing hospitalization; 3) results in persistent or significant disability/incapacity; 4) constitutes a congenital anomaly or a birth defect and/or; 5) is medically significant such that it may jeopardize the subject, and may require medical or surgical intervention to prevent one of the outcomes listed above.

A summary of all adverse events (not just those considered related to the DC vaccine) will be kept which will categorize the event by organ system, relationship to treatment, its grade of severity, and resolution. The PI will periodically review the collective adverse events with the intention of identifying any trends or patterns in toxicity. If any such trends are identified, depending on their severity and frequency, a protocol amendment will be considered.

All adverse events which are serious and unexpected (as defined by 21CRF312.32[a]) should be reported immediately to [name] ([contact]) or his designee [contact]). Fatal or life-threatening, unexpected adverse events that are related or possibly related to the research will be reported to the FDA by telephone, facsimile, or in writing as soon as possible, but no later than 7 calendar days after first knowledge by the sponsor followed by as complete a report as possible within 8 additional calendar days. Serious, unexpected adverse events that are related or possibly related to the research and are not fatal or life-threatening will be reported to the FDA by telephone, facsimile, or in writing as soon as possible, but no later than 15 calendar days after first knowledge by the sponsor.

All adverse events that are considered serious, unanticipated, and related or possibly related to the research (as defined by 21CRF312.32[a]) will be reported to the Duke University Medical Center IRB using the appropriate SAE report form. At the time of the annual progress report to the Duke University Medical Center IRB, a summary of the overall toxicity experience will be provided.

